### 89 1 Operational Plan for Implementation

#### 90 1.1 Study Summary

91 This protocol describes Strategies and Opportunities to STOP Colorectal Cancer in Priority Populations, 92 STOP CRC, a cluster-randomized pragmatic study designed to increase rates of colorectal cancer (CRC) 93 screening in safety-net primary care practices. STOP CRC is a collaboration of The Center for Health 94 Research at Kaiser Permanente Northwest (CHR), Group Health Cooperative Research Institute, and OCHIN, 95 the nation's largest network of safety-net practices. OCHIN-member clinics are linked by the same 96 electronic health record (EHR). Our overall goal is to increase CRC screening rates in large numbers of 97 diverse patients by devising and testing an intervention that uses a low-cost fecal test. We plan do this in 98 partnership with 24 OCHIN-member clinics. This project promotes the use of fecal immunochemical testing 99 (FIT) for colorectal cancer screening, as it has been shown to be an effective population-based strategy for 100 increasing CRC screening rates. While colonoscopy is recommended by some professional organizations, it may 101 not be optimal for primary screening as serious adverse complications are not uncommon (1 in 250), endoscopic 102 capacity is limited, procedure costs are high, access is limited, and many patients prefer alternative tests, 103 particularly for some minority groups. (1,2) For these reasons, STOP emphasizes primary screening using fecal 104 testing, with colonoscopy follow-up for positive tests. 105

106 The primary objectives in STOP CRC are the following:

Primary Aim 1. Assess the effectiveness of a large-scale, two-arm CRC screening program among
 diverse Federally Qualified Health Center (FQHC) patients and assess differences in CRC screening
 outcomes across patient subgroups – e.g. age, sex, insurance status, Hispanic ethnicity/race. The
 intervention will consist of:

- An automated data-driven, EHR-linked program for mailing FIT kits (with linguistically appropriate pictographic instructions and return postage) to patients due for CRC screening
- 113 **Primary Aim 2.** Assess the costs and long-term cost-effectiveness of the automated program.
- 114 The secondary objectives are to:
- Secondary Aim 1. Assess adoption, implementation, reach and potential maintenance and spread of
   the program, using a mixed-method rapid assessment process, field notes, and other ethnographic
   data.

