## 505 2.3.2 Secondary Outcomes

[figure not shown]
- 506 Our secondary outcomes are provided below:
- For participants who received a FIT kit, the probability of returning it within 3, 6, 9 and 12 months of its being sent as well as time to FIT/FOBT return
   Receipt of any CRC screening (fecal test, sigmoidoscopy or colonoscopy) during the follow-
  - NQF score (proportion of those age 50-74 with a colonoscopy within 10 years, flexible
  - sigmoidoscopy within 5 years, and FOBT/FIT within 1 year) as assessed relative to the oneyear pre and each of the first two years post randomization
    - Presence of a positive FIT/FOBT among those who return a FIT kit
    - Referral for a colonoscopy among those with a positive FIT/FOBT
    - Completion of a colonoscopy following a positive FIT/FOBT

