745 cancers, screening can reduce the cost of treating cancer in those who were destined to develop the 746 disease, denoted as Ccancer. Total costs for a particular screening + promotion program A are: 747 748 CA = [CsceenA + CpromoteA - CcancerA ] 749 750 751 By reducing the incidence of advanced cancers, screening technologies increase the number of life years 752 (LY) for a population, less any morbid or mortal side effects of the screening intervention. Thus, in 753 comparing two screening promotion programs, the incremental cost-effectiveness of new program A versus 754 the established program B is: 755 756 Incremental Cost-Effectiveness Program A = (CA – CB)/(LYA – LYB) 757 758 We will report cost-effectiveness as cost per additional screenee and cost per LY gained (note that cost per 759 additional screenee does not include CsceenA or CcancerA and the denominator is total number of persons 760 in each population obtaining screening rather than LY). Since realization of the benefits of screening 761 promotion programs will take years or even decades, direct evaluation of the impact of promotion from the 762 trial on LY is infeasible. 763 764 Costs associated with promotion (Cpromotion): We will document the non-research costs associated with 765 implementing the CRC screening intervention. These include associated fixed costs (i.e., those unrelated to 766 the size of the target group) and variable costs. Fixed costs include implementation costs (e.g., staff 767 training), maintenance, office space used in the clinic, equipment and materials (e.g., computers), and 768 telephone. Variable costs include labor costs associated with delivering the interventions as well as 769 materials distributed to the participants (e.g., FITs). Accounting systems will be used as a source of data on 770 the cost of equipment and supplies (e.g., printing). To estimate labor costs associated with delivering the 771 intervention, clinic staff will record the time they spend delivering intervention components (e.g., for 772 placing FIT orders) on staff logs. Fixed and variable costs will be amortized to determine the average 773 expenditure associated with delivering an intervention (e.g., mailing costs) to the study population 774 (Cpromotion). 775 776 **Costs of colorectal cancer screening (Cscreen).** Each individual who obtains screening will be assigned an 777 associated cost, including the time-costs associated with screening, and costs for evaluation of true and 778 false positives. Test and evaluation costs will be based on reimbursements from nationally standardized 779 databases (e.g., Medicare reimbursements). As this is a home-based test, no time will be associated with 780 transportation. Time spent in screening will be valued by national wage rates for individuals of the study 781 population's age group and ethnicity. (This time is anticipated to be low.) 782 783 Estimating LY gained and quality-adjusted LY. Our trial is not designed to estimate differences in CRC rates 784 or survival for the screened population. These will need to be estimated through modeling. We propose 785 building a Markov state transition model to estimate years of life gained and quality-adjusted LY. Three 786 states are accounted for: healthy, CRC, and death. The healthy and CRC states are assigned a utility weight 787 for calculating quality-adjusted LY are calculated. 788 We start with simplifying assumptions that all individuals who start screening as a result of the program will 789 continue and those who screen have no risk for developing invasive CRC. Risk of death in each year will be 790 determined from life tables; risk of CRC in the unscreened population will be based on epidemiological 791 data. Those who develop CRC face a risk of death (from other causes) or death from CRC. Disease-specific 792 survival rates for CRC will be based on Surveillance Epidemiology and End Results (SEER) survival data.(3). A-25

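### Section 2.6 defines life-years gained net of screening harm, but no component named for its Markov model carries such a harm, so life-years and quality-adjusted life-years come out gross of follow-up colonoscopy complications

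*Protocol*

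**What the plan says.** Section 1.1 of the protocol sets Primary Aim 2: "Assess the costs and long-term cost-effectiveness of the automated program". When arguing for FIT over primary colonoscopy, it says of colonoscopy that "serious adverse complications are not uncommon (1 in 250" by its own figure. It then describes the chosen strategy as primary fecal "testing, with colonoscopy follow-up for positive tests".

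Section 2.6 says that screening adds life-years to a population "less any morbid or mortal side effects of the screening intervention", and goes on to use the life-year difference between programs as the denominator of the incremental cost-effectiveness ratio. Because the trial cannot observe survival, a Markov model is to supply life-years and quality-adjusted life-years. In it, three "states are accounted for: healthy, CRC, and death". Utility weights are attached to the healthy and CRC states. Death comes from life tables and, once in the CRC state, from other causes or from CRC. Two simplifying assumptions are named as a start: those who begin screening continue, and those who screen cannot develop invasive CRC.

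On the cost side, each screened person is assigned a cost "including the time-costs associated with screening, and costs for evaluation of true and" false positives. Complication costs are not named. One-way and multiway sensitivity analyses on changes in assumptions are planned, without a list of parameters.

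Section 2.3.2 lists the positive-test proportion and "Completion of a colonoscopy following a positive FIT/FOBT" among the secondary outcomes, so the trial will record the inputs that determine how many follow-up colonoscopies the program generates.

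**The concern.** The section defines a net quantity and then specifies a model whose stated parts produce a gross one. This is more than missing detail: the reported cost per life-year would carry a definition that its calculation does not meet.

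The missing harm is one that the protocol itself stresses when choosing the screening test. The model pays for the work-up of positive tests and credits screening with complete prevention of invasive CRC, while the complication of that work-up appears nowhere. If the program leads to more colonoscopies than usual care, the omission makes cost per life-year and cost per quality-adjusted life-year look somewhat better than the definition allows. Both feed the second of the trial's two primary aims.

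**Working it through.** **Step 1. Definition against model components.** The 1 in 250 is a cited input and cannot be re-derived, so the check starts from the text of section 2.6.

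| Component named in section 2.6 | Content | Screening harm in it? |
|---|---|---|
| Life-year definition | gain less side effects | yes, to be subtracted |
| States | healthy, CRC, death | none named |
| Death, healthy state | life tables | none; no procedure deaths added with more screening |
| Death, CRC state | other causes or CRC | none |
| Utility weights | healthy and CRC | no loss for a complication |
| Starting assumptions | continued screening; no invasive CRC if screened | none |

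The number of states does not settle the matter by itself. Harm could sit within three states as an added healthy-to-death probability or a one-off utility loss. The gap follows because the death sources and utility weights omit it as well. Relaxing either starting assumption still leaves the harm term at zero.

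**Step 2. Complications per round.** Inputs: 1 in 250 per colonoscopy (section 1.1); positivity of 5% to 10.5% and colonoscopy completion of 50% to 100%, both assumed. The 10.5% is only the clinic-level value in the mock report of section 4.2.3 (4 of 38 kits).

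Complications per 1000 screenees = 1000 × positivity × completion ÷ 250.

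- Low: 1000 × 0.05 × 0.5 ÷ 250 = 0.10
- High: 1000 × 0.105 × 1.0 ÷ 250 = 0.42

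The model as written counts 0 in each case.

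**Step 3. Scale of the life-year effect.** Only fatal complications change life-years, and the protocol gives no fatality. For scale, a three-state cohort was run with the plan's 3% discounting and no CRC if screened. Everything else is assumed:

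- start at age 57, followed to 100, with annual testing up to age 74;
- other-cause death 0.0045 × 1.09^(age − 55);
- CRC incidence in the unscreened 0.001 × 1.05^(age − 57);
- excess death in the CRC state 8% a year, CRC utility 0.7;
- positivity 6.5%, completion 80%, so 1000 × 0.065 × 0.8 ÷ 250 = 0.208 complications per 1000 per round, in the screened arm only;
- one-off utility loss of 0.02 to 0.1 per complication.

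| Share of complications fatal (assumed) | Life-years gained per 1000 | Reduction in life-years | Reduction in QALYs |
|---|---|---|---|
| no harm term | 171.39 | – | – |
| 0% | 171.39 | 0% | 0.02% to 0.11% |
| 1% | 170.97 | 0.24% | 0.19% to 0.29% |
| 5% | 169.33 | 1.20% | 0.88% to 0.97% |
| 10% | 167.28 | 2.39% | 1.73% to 1.82% |

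The reduction scales almost in proportion to the complication rate. At the high end of Step 2 (0.42 ÷ 0.208 = 2.02 times as many) with 10% fatality it is 4.8%. It also roughly doubles if the assumed CRC incidence is halved, because the benefit being eroded is then half as large.

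**The case against.** The strongest reply is that section 2.6 is a sketch. It speaks of a model still to be built and of assumptions to start from, and it gives no cycle length or utility values. On that view the life-year definition is the requirement, and the parameter list comes later. This is fair as far as it goes: nothing forbids adding harm. But the section does list the sources of death and the utility weights, and those lists do not deliver the quantity it defines.

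Several stronger readings are tempting and are not supported:

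- **That a three-state model cannot carry harm.** It can, as noted in Step 1.
- **That the planned sensitivity analyses cannot reveal the omission.** They are open-ended. Harm could be added to them, although nothing written requires it.
- **That complication costs are definitely excluded.** The cost description is introduced as non-exhaustive, and the cost of evaluating positives could be read to cover complications of that evaluation.
- **That return on investment is biased.** It rests on healthcare expenditures and program costs, so it is affected only if complication costs are left out of those expenditures.
- **That every additional screenee adds a full increment of harm.** Usual care also generates colonoscopies; any CRC screening is an outcome in both arms. Where FIT replaces a primary colonoscopy, the net harm is smaller. Steps 2 and 3 do not net this out.

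It also stands that the 1 in 250 was quoted against primary colonoscopy, so applying it to colonoscopy after a positive FIT is an assumption.

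**Conclusion.** The inconsistency is real and its likely consequence is small. As written, section 2.6 yields life-years and quality-adjusted life-years gross of follow-up colonoscopy complications, although it defines the benefit net of them. The omission probably favours the program slightly, provided that the program produces more colonoscopies than usual care.

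The uncounted harm is about 0.1 to 0.4 serious complications per 1000 screenees per round. The life-year effect is 0% to 2.4% in the illustrative model and 4.8% at its less favourable corner; it is probably no more than a few percent. These figures rest on assumed positivity, completion, fatality, mortality and CRC incidence. Complication fatality matters most, and the protocol does not give it.

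The FIT completion outcome and the power calculation are untouched. So is cost per additional screenee, from which section 2.6 excludes screening and cancer costs. This is a cheap improvement of low-to-moderate priority.

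**What to change.** In section 2.6, add a colonoscopy-complication term to the model in both arms, applied to the colonoscopies that each arm generates. An excess death probability plus a one-off utility loss fits within the three states; add a complication cost to the screening cost.

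For the base case, use the positivity and follow-up colonoscopy completion observed in the trial together with the protocol's 1 in 250. Section 2.4.1 already warns that returned kits will be few in many control clinics, so say how an imprecise control-arm estimate will be handled. Take fatality, utility loss and cost from published sources, and name the complication rate as a parameter of the one-way and multiway sensitivity analyses.

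If the sponsor prefers not to extend the model, the minimum is a sentence stating that life-years and quality-adjusted life-years are reported gross of screening harm, with the definition in section 2.6 brought into line.

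The cost is a few literature inputs and a slightly less favourable ratio. No new patient data or procedures are needed, and the change concerns the economic model only.

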#### 323 324 **1.9 Maintenance**

The second year of the intervention will be considered a maintenance year. Maintenance will comprise the following activities:

327 328

329

330

331

- Health Center leaders will choose whether to maintain the program in YRO2 at the intervention sites;
- Those that maintain will document any adaptations that they make to the program, and we will capture this during the qualitative Rapid Assessment Process (See Section 2.8)
- Health Center leaders will also choose whether to roll-out the program in YR02 to usual care clinics within their health center.
  - Health Center leaders may also opt to roll-out the program in YR02 to additional clinics in their health center that did not participate in the study (neither intervention or usual care).
- 335 336

334

The research team will document maintenance at the clinic- and patient-levels. Clinic-level maintenance
will assess the number of clinics that maintained the program in Year 02, overall and by intervention status
(including clinics that were neither assigned to intervention or usual care). Patient-level maintenance will
assess the proportion of patients who completed fecal testing in both years of the program.

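### The base case of the life-year model sets continuation of screening and protection against cancer at their most favourable values, so modelled life-years gained are biased upward

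*Protocol*

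**What the plan says.** Section 1.1 makes the program's costs and long-term cost-effectiveness Primary Aim 2, and section 2.6 treats this as the second primary outcome. Because life-years cannot be observed within the trial, section 2.6 proposes "building a Markov state transition model to estimate years of life gained and quality-adjusted LY", in which three "states are accounted for: healthy, CRC, and death".

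The section introduces its inputs with "We start with simplifying assumptions": that "all individuals who start screening as a result of the program will" "continue and those who screen have no risk for developing invasive CRC". It gives no further step and no other value for either quantity. It then sets a 3% annual discount rate and commits to one-way and multiway sensitivity analyses of the cost-effectiveness ratios, without listing parameters or ranges.

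Two measures of cost-effectiveness are to be reported: cost per additional screenee and cost per life-year gained. Return on investment is added, based on savings less program costs.

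Elsewhere, the protocol collects data on both modelled quantities. Section 1.9 will "assess the proportion of patients who completed fecal testing in both years of the program". Section 2.3.2 lists as a secondary outcome "Completion of a colonoscopy following a positive FIT/FOBT". Section 2.6 does not say that either feeds the model.

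**The concern.** Continuation cannot exceed 100% and cancer risk cannot fall below zero. The base case therefore sits at the end of the range that favours the program on both parameters. Any other value lowers the modelled life-years gained, provided that more people are screened in the intervention arm. The headline would be a best case presented where a reader expects a central estimate, and sensitivity analyses could move it in one direction only.

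At stake are base-case life-years and QALYs gained, cost per life-year, and the averted cancer cost that enters both total cost and return on investment. The trial's effectiveness result and cost per additional screenee are not at stake.

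**Working it through.** The protocol states no life-year or cost-per-life-year figure, so there is none to reproduce. The check concerns direction and plausible size.

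**Direction.** Let r be the proportion of cancers prevented while a person screens, and k the proportion of screeners who continue each year. Section 2.6 sets r = 1 and k = 1. Cancers averted rise with both, so life-years gained are highest at these values.

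**First-order size for r.** Cancers averted are proportional to r, so life-years gained at r are about r times those at r = 1, and the overstatement is about 1/r. At r = 0.8 this is 1/0.8 = 1.25; at r = 0.4 it is 1/0.4 = 2.5.

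**Cohort model.** From the protocol: the three states and the 3% discount rate. Assumed: start age 58; cancer incidence i(t) = 0.001 × 1.06^t; other-cause mortality d(t) = 0.007 × 1.09^t; excess mortality with cancer 10% per year; 42 annual cycles; r from 0.4 to 0.8. With S healthy screeners, U healthy non-screeners and C with cancer:

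- new cancers in year t = S·i(t)·(1 − r) + U·i(t);
- healthy survivors are multiplied by 1 − d(t); those already with cancer also by 1 − 0.10;
- a share 1 − k of surviving screeners moves from S to U;
- discounted life-years = sum of (S + U + C)/1.03^t;
- life-years gained = result starting with S = 1, minus result starting with U = 1.

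With k = 1:

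| r | Life-years gained per additional screenee | Overstatement at r = 1 | Same, if excess mortality is halved to 5% in cancers among screeners |
|---|---|---|---|
| 1.0 | 0.1771 | – | – |
| 0.8 | 0.1411 | 1.25 | 1.15 |
| 0.6 | 0.1054 | 1.68 | 1.35 |
| 0.4 | 0.0700 | 2.53 | 1.62 |

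The ratios hardly depend on incidence. With incidence starting at 0.05% or 0.10%, rising 7% a year and capped at 0.6%, the base case is 0.0994 or 0.1943 life-years, and r = 0.5 leaves 49.7% or 49.4% of it.

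**Cost per life-year, zero-risk assumption.** Residual cancers remove life-years and averted cancer cost but save essentially no screening cost. At an assumed 60 dollars a year for screening, and counting nothing else, cost per life-year is about 5,931 at r = 1, 7,410 at r = 0.8 and 14,803 at r = 0.4: ratios of 1.25 and 2.50. Section 2.6 subtracts averted cancer cost from total cost. That saving also shrinks as r falls, which moves the result the same way.

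**Cost per life-year, continuation assumption.** With r = 1, k = 0.9 leaves about 40–42% of the life-years across the three incidence settings, and k = 0.7 leaves about 16–17%. Screening costs stop as well: in the first setting cost per life-year goes from 5,931 to 5,870 (k = 0.9) or 6,118 (k = 0.7). Across all three settings the change runs from about 1% lower to 13% higher. A one-off promotion cost, not counted here, would add to this.

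**Cost per additional screenee.** Section 2.6 excludes screening and cancer costs from this measure and uses persons screened as its denominator. Neither r nor k enters.

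**The case against.** The strongest reply is that section 2.6 is candid. It labels these as simplifying assumptions from which the model starts, and it promises sensitivity analyses to changes in assumptions, which would naturally cover the two it has just named. Parameter lists and ranges are often fixed in a later analysis plan, and their absence is not an error. This stands in part: the assumptions are not concealed and need not be final. But no other base case is stated, and one-sided sensitivity analyses leave the headline at the best case.

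A reader might infer more than the text supports:

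- **That one returned kit confers lifelong freedom from cancer.** The text says only that people continue, and gives zero risk to those who screen. It does not say lifelong, so the 50–74 eligibility range is no contradiction.
- **That the protocol contradicts itself by measuring repeat testing and colonoscopy completion.** Measuring a quantity does not contradict a declared simplification of it. The choice that health centers have about a second year concerns clinic-level maintenance.
- **That the overstatement is many-fold.** Figures of about 7–14 fold arise with an assumed 70% annual continuation, screening that ends at 75 and only 40–80% prevention. They apply to life-years; the continuation part hardly moves cost per life-year.
- **That having no cancer stages is a separate error.** Section 2.6 does attribute benefit to fewer advanced cancers ("By reducing the incidence of advanced cancers, screening technologies increase the number of life years"). With zero cancer among screeners, though, there is nothing to detect earlier. Stage matters only once residual risk is allowed, and crediting it reduces the overstatement.

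**Conclusion.** The concern holds for the base case. Both parameters are at their favourable bound, so modelled life-years and QALYs gained are biased upward. The zero-risk assumption also biases cost per life-year and the averted cancer cost in return on investment toward the program. The direction follows from the stated assumptions if the intervention raises screening.

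The size is illustrative. If screening prevents 40–80% of cancers, life-years gained are overstated about 1.25–2.5 fold, or about 1.15–1.6 fold if earlier detection halves excess cancer mortality. Apart from the discount rate and the three states, every input is an assumption, and the prevention range matters most. The point is worth correcting because it touches a primary aim and the remedy is cheap, but it affects only part of that aim.

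**What to change.** In section 2.6, replace the starting assumptions with a base case that has:

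- a residual cancer risk among screeners, from a stated and sourced risk reduction below 100%, scaled by the trial's observed colonoscopy completion after a positive fecal test. If the source already reflects incomplete follow-up, do not scale twice;
- continuation below 100%, informed by the two-year repeat-testing proportion and varied widely. One repeat interval is limited evidence, and because health centers may drop the program in the second year, it mixes clinic discontinuation with patient adherence.

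Name both parameters, with ranges, in the planned one-way and multiway sensitivity analyses. Keep full continuation with no cancer risk as a labelled best-case scenario. Splitting cancer by stage is optional; if it is omitted, say that earlier detection is not credited.

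The cost is modest extra modelling, an outside source for the risk reduction, and a less favourable headline cost per life-year. No new trial data are needed.
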